10.5.3.2 Adverse events (AEs)

Summary tables for adverse events (AEs) will include only AEs that started or worsened during the on-treatment period, the **treatment-emergent** AEs. However, all safety data (including those from the pre and post-treatment periods) will be listed and those collected during the pre-treatment and post-treatment period are to be flagged. The incidence of treatment-emergent adverse events (new or worsening from baseline) will be summarized by system organ class and or preferred term, severity (based on CTCAE version 4.03 grades), type of adverse event, relation to study treatment.

Serious adverse events, non-serious adverse events and adverse events of special interest (AESI) during the on-treatment period will be tabulated.

All deaths will be listed.

All AEs, deaths and serious adverse events (including those from the pre and post-treatment periods) will be listed and those collected during the pre-treatment and post-treatment period will be flagged.

10.5.3.3 Laboratory abnormalities

Grading of laboratory values will be assigned programmatically as per NCI Common Terminology Criteria for Adverse Events (CTCAE) version 4.03. The calculation of CTCAE grades will be based on the observed laboratory values only, clinical assessments will not be taken into account.

CTCAE Grade 0 will be assigned for all non-missing values not graded as 1 or higher. Grade 5 will not be used.

For laboratory tests where grades are not defined by CTCAE v4.03, results will be categorized as low/normal/high based on laboratory normal ranges.

The following summaries will be generated separately for hematology, and biochemistry and urinary laboratory tests:

- Listing of all laboratory data with values flagged to show the corresponding CTCAE v4.03 grades if applicable and the classifications relative to the laboratory normal ranges

For laboratory tests where grades are defined by CTCAE v4.03

- Worst post-baseline CTCAE grade (regardless of the baseline status). Each patient will be counted only once for the worst grade observed post-baseline.
- Shift tables using CTCAE v4.03 grades to compare baseline to the worst on-treatment value

For laboratory tests where grades are not defined by CTCAE v4.03, shift tables based on the low/normal/high/ (low and high) classification will be used to compare baseline to the worst on-treatment value. In addition to the above mentioned tables and listings, other exploratory analyses, for example figures plotting time course of raw or change in laboratory tests over time or box plots might be specified in the SAP.

10.5.3.4 Other safety data

ECG

ECG data will be summarized with

- shift table baseline to worst on-treatment result for overall assessments
- Number and percentage of patients with clinically notable QT/QTcF interval values will be summarized.
- listing of ECG evaluations for all patients with at least one abnormality.

Vital signs

Vital signs (supine BP, HR & temperature) reporting of results will include

- shift table baseline to worst on-treatment result
- table with descriptive statistics at baseline, one or several post-baseline time points and change from baseline to this/these post-baseline time points.

Tumor volume

For tumor volume evaluated by MRI (or CT) scanning, descriptive summary of actual tumor volumes as well as its actual and percent change from baseline will be provided. The number and percentage of patients with newly occurring measurable tumor and/or new evidence of tumor invasion into surrounding structures during the study will be calculated. For MRI (or CT) images that are not interpretable for tumor volume, the longest dimension (in mm) will be summarized instead.

10.5.3.5 Supportive analyses for secondary objectives

Not applicable.

10.5.3.6 Tolerability

Tolerability will be studied in terms of dose reductions or drug interruption due to an AE.

10.5.4 Pharmacokinetics

The PAS will be used in all pharmacokinetic data analysis and summary statistics.

As sparse pharmacokinetic sampling is performed in this study, traditional non-compartmental analysis will not be performed to calculate pharmacokinetic parameters. Plasma concentration data of LCI699 will be listed by patient, visit, incident dose and nominal sampling times. Descriptive statistics of plasma concentrations will be provided by incident dose, visit and nominal sampling times. Graphical depiction (mean and individual) for LCI699 concentrations and/or profiles (if applicable) during the course of the study will be performed by incident dose and visit. Additional details on PK data analysis will be specified in the SAP.

PK data generated from this study will be used in conjunction with PK data from other clinical studies in population PK assessment. Patient demographics (e.g. age, gender, ethnicity, weight) will be explored as covariates, if appropriate. The broad principles outlined in the FDA “Guidance for Industry: Population Pharmacokinetics” will be followed during the population PK analysis. The results of population PK assessment will be presented in a separate report.

[(China only) Plasma concentration data of LCI699 will be listed by patient, visit, incident dose and nominal sampling times. Descriptive statistics of plasma concentrations will be provided by incident dose, visit and nominal sampling times. For the extensive sampling profiles, graphical depiction (mean and individual) for LCI699 concentrations and/or profiles (if applicable) during the course of the study will be performed by incident dose and visit. Descriptive statistics will be reported for all PK parameters (including AUC_{last}, AUC_{inf}, C_{max}, T_{max}, T_{1/2}, Cl/F, V_z/F) for LCI699 from the extensive sampling profiles. For sparse sampling data, traditional non-compartmental analysis will not be performed. PK data from this study will be used in conjunction with PK data from other clinical studies in population PK assessment.]

10.5.4.1 Data handling principles

Plasma concentrations of LCI699 will be expressed in ng/mL. Missing concentration values will be labeled as such in data listings. Concentrations below the limit of quantitation (LLOQ) will be treated as zero in summary statistics and reported as zero in data listings.

[REDACTED]

10.5.6 Resource utilization

Not Applicable.

10.5.7 Patient-reported outcomes

The CushingsQoL score is identified as the primary PRO variable of interest. EQ-5D utility index and visual analogue scale (VAS) scores, and Beck Depression Inventory-II (BDI) total score are identified as secondary PRO variables of interest. The FAS will be used for analyzing PRO data. No multiplicity adjustment will be applied.

[figure not shown]
Change from Week 24 in the CushingsQoL score during Study Period 3 will be analyzed using a linear mixed effect model for longitudinal data to assess the treatment effect over time including terms for treatment, stratification factors, time of visit (in weeks counting from the time of randomization to the time of a particular post baseline measurement), treatment by time of visit interaction, and Week 24 score. The differences in least square means between LCI699 and placebo group, and the corresponding 2-sided 95% confidence interval (CI) at each timepoint will be presented. Descriptive statistics will be used to summarize the raw and absolute change from baseline for the scores at each scheduled assessment during the core and extension periods (Week 72, 96, and EOT extension) of the study.

[figure not shown]
Similar analyses will be performed for EQ-5D utility index and visual analogue scale (VAS) scores, and Beck Depression Inventory-II (BDI) total score.

Missing items data in a scale will be handled based on each instrument manual. Additional details for handling missing items data will be specified in the analysis plan for instruments with no missing data handling criteria in the instrument manual.

No imputation will be applied if the total scores are missing at a visit. Patients with Week 26 and at least one non-missing post-Week 24 assessments during the Study Period 3 will be included in the linear mixed effect model analysis. All available data until completion or early discontinuation during Period 3 will be used in the linear mixed effect models analyses which assume that the missing scores at any time point are missing-at-random. Additional sensitivity analysis may be performed to assess the possible violation of missing-at-random assumption for the missing data mechanism if deemed appropriate. Details will be specified in the SAP.

[REDACTED]

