To assess the change in Patient-Reported Outcomes (Health-Related Quality of Life) during the core and extension periods of the study.	
 Change in standardized score of CushingQoL, Beck Depression Inventory-II, and EQ-5D-5L, from baseline to Week 24 and Week 48. Change in standardized score of CushingQoL, Beck Depression Inventory-II, and EQ-5D-5L, from the randomization (Week 26) to the end of randomized withdrawal period (Week 34), or the last measurement prior to early discontinuation, whichever occurs earlier. Change from baseline in standardized score of CushingQoL, Beck Depression Inventory-II, and EQ-5D-5L, from baseline to Week 72, 96 and the EOT extension 	
To assess the change from baseline in the physical features of Cushing's disease by photography at Week 12, 24, 34, 48, and during the extension phase.	Categorical change from baseline to Week 12, 24, 34, 48, during the extension at week 72 and EOT extension in each of the following clinical signs of Cushing's disease by photography: facial rubor, hirsutism, striae, supraclavicular fat pad, dorsal fat pad, proximal muscle wasting (atrophy), central (abdominal) obesity, and ecchymoses (bruises).	
To assess the change from baseline in bone mineral density by DXA scan at the lumbar spine and total hip at Week 48 and the last available assessment.	Actual and percent change from baseline to Week 48 and the last available assessment in bone mineral density as measured by DXA scan at the lumbar spine and total hip	
To assess the time-to-escape.	Time-to-escape is defined as the time (in days) from the first mUFC \leq ULN to the first mUFC results $> 1.5 \times$ ULN with at least 2 individual UFC results $> 1.5 \times$ ULN.	

Objective	Endpoint	Analysis
To assess general safety and AEs of special interest	Adverse events and laboratory abnormalities will be assessed using the National Cancer Institute-Common Toxicology Criteria (NCI-CTC) grading scale (version 4.03). AEs of special interest, as reported by the investigator, or by laboratory evaluation, ECG, Holter recording, and pituitary MRI.	
To evaluate exposures of LCI699 in patients with Cushing's disease	Plasma concentrations (predose, 0.5 h, 1.5 h, and 3.5 h post-dose) of LCI699	

4 Study design

[figure not shown]

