2.1.1.2 Baseline

For efficacy and safety evaluations (e.g. laboratory assessments and vital signs): the last available pre-dose assessment within 35 days prior to or on Study Day 1 (before the first dose of LCI699) is taken as the “baseline” assessment; the last available assessment within 21 days prior to the first dose of randomized treatment (LCI699 or Placebo) is taken as the “randomization” assessment; If patients have no value as defined above, the baseline/randomization result will be considered missing.

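### The Period 3 patient-reported-outcome model measures change from Week 24, but the endpoint is change from randomization at Week 26, and the model's entry rule fits neither reference cleanly

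*Protocol*

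**What the plan says.** **The model (Protocol 10.5.7).** "Change from Week 24 in the CushingsQoL score during Study Period 3 will be analyzed using a linear mixed effect model". The terms include "treatment by time of visit interaction, and Week 24 score". Time is measured "in weeks counting from the time of randomization to the time of a particular post baseline measurement". On entry: "Patients with Week 26 and at least one non-missing post-Week 24 assessments during the Study Period 3 will be included". On data: "All available data until completion or early discontinuation during Period 3 will be used". The output is the difference in least-squares means with a 95% confidence interval at each timepoint. Similar analyses follow for the EQ-5D index, the EQ-5D VAS and BDI-II, without multiplicity adjustment. The section does not say whether time is categorical or continuous.

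**The endpoint (Protocol Table 3-1).** The change is taken "from the randomization (Week 26) to the end of randomized withdrawal period (Week 34), or the last measurement prior to early discontinuation". SAP Table 1-1 uses the same reference point.

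**The reference value (SAP 2.1.1.2).** For efficacy and safety evaluations, the randomization value is "the last available assessment within 21 days prior to the first dose of randomized treatment".

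**The schedule.** Protocol Tables 7-2 and 7-16 mandate the questionnaires at Weeks 24, 26, 28, 30, 32 and 34, before dosing at the visit. Randomization takes place at Week 26 before dosing (6.5.2). All patients stay on open-label LCI699 between Weeks 24 and 26 (4.1.2). Period 3 runs from Week 26 to Week 34 (4.1.3).

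**The concern.** A score is collected on the day of randomization, before the first randomized dose, and both endpoint tables name that day as the reference. The model passes it over for a score taken two weeks earlier. The endpoint and its analysis therefore do not match, and the adjustment uses the more distant of two available pre-treatment scores.

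The section also fails to settle the role of the Week 26 score. It is required for entry, it marks time zero, and yet it is neither the reference nor the covariate. If it is treated as an outcome, the model contains a visit at which randomized treatment cannot yet have acted. How much that matters depends on how time is fitted, which the section leaves open.

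**Working it through.** The plan gives no sample size, power or expected effect for this model, so there is no figure to reproduce. The check sets the texts side by side and then illustrates the consequences.

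**1. Which score is the reference?** Week 24 is Day 169 and Week 26 is Day 183, a gap of 183 − 169 = 14 days. Under the 21-day window of SAP 2.1.1.2, the Week 26 pre-dose score is the randomization value when present. Week 24 qualifies only as a fallback. I take the rule to cover the questionnaires as efficacy evaluations; it does not name them.

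**2. Does the entry rule fit the model?**
- A patient with scores at Weeks 26 to 34 but none at Week 24 meets the entry rule, yet has neither the outcome (change from Week 24) nor the covariate.
- A patient with scores at Weeks 24 and 28 to 34 but none at Week 26 is excluded, although the model as written could use every score.
- Period 3 starts at Week 26, all available Period 3 data are used, and the second entry condition needs only a score after Week 24. The pre-dose Week 26 score can be read to satisfy it.

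**3. Bias with categorical visits.** Both candidate references precede randomized dosing. Under randomization, the arms have the same expected score at each. The expected between-arm difference at Weeks 28 to 34 is therefore the same from either reference, and the visit-specific contrasts are unbiased.

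**4. Precision at Week 34.** Assumptions:
- 33 per arm, as planned in Protocol 10.8.
- SD = 10.1 / 0.5 = 20.2, from the literature minimal important difference in SAP 2.11.1. That figure refers to the four-week recall, whereas this trial uses one week.
- Correlation r between Weeks 26 and 34 of 0.5 to 0.8, decaying exponentially with time. The Week 24 to Week 34 correlation is then r^(10/8).

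SE = 20.2 × √(1 − R²) × √(2/33), where R is the correlation of the covariate with the Week 34 score. Power is for a true difference of 10.1 points, two-sided 5%.

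| r (Week 26) | R (Week 24) | SE, Week 26 covariate | SE, Week 24 covariate | Ratio | Power, Week 26 | Power, Week 24 |
|---|---|---|---|---|---|---|
| 0.5 | 0.420 | 4.31 | 4.51 | 1.05 | 65% | 61% |
| 0.6 | 0.528 | 3.98 | 4.22 | 1.06 | 72% | 67% |
| 0.7 | 0.640 | 3.55 | 3.82 | 1.08 | 81% | 75% |
| 0.8 | 0.757 | 2.98 | 3.25 | 1.09 | 92% | 87% |

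**5. Week 26 kept as an outcome, time as a straight line.** Let the true difference be 0 at Week 26 and a constant 1 from Week 28. With t = 0, 2, 4, 6, 8 weeks and d = 0, 1, 1, 1, 1:
- The mean of t is 4 and the mean of d is 0.8.
- Slope = Σ(t − 4)d / Σ(t − 4)² = 4 / 40 = 0.1; intercept = 0.8 − 0.1 × 4 = 0.4.
- Fitted differences are 0.4, 0.6, 0.8, 1.0 and 1.2 at Weeks 26, 28, 30, 32 and 34.

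Without Week 26, the fit gives 1.0 at every visit. If the true difference grows linearly from zero at Week 26, the fitted values are correct with or without that visit.

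**The case against.** The strongest reply is that little harm follows. Both weeks precede randomized treatment, all patients take the same drug between them, and the plan reports visit-specific differences. This stands. A reader might infer that the model is biased or fails to estimate a treatment effect; with categorical visits, the documents do not support that.

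A reader might also infer that the treatment effect is diluted by one fifth, because one of five Period 3 visits (26, 28, 30, 32, 34) carries no effect: 4/5 = 0.8. That would apply to an average over the five visits, and 10.5.7 plans no such average.

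Nor is it stated that Week 26 is an outcome visit, or that a patient with only that score qualifies. If the Week 26 score met the second entry condition, that condition would be redundant, so a Week 26 score plus a later one is a natural reading. The sentence may be an incomplete edit. What stands is that the text permits more than one reading.

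Larger precision losses can be produced by choosing other correlations. With 0.7 for Week 24 and 0.8 for Week 26, the residual variance ratio is (1 − 0.49) / (1 − 0.64) = 1.42. The documents give no correlations, so neither that figure nor the table above is more than an illustration.

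Finally, the supplied SAP covers the Final CSR. It plans only descriptive change-from-baseline summaries for the questionnaire scores (2.11.4), and its introduction refers the core-phase analyses to a separate SAP dated 06-Jul-2018. That document may have resolved the point. Nothing supplied does so.

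**Conclusion.** The inconsistency is explicit and should be corrected: Week 24 in the model, Week 26 in both endpoint tables, and an entry rule that requires the score the model does not use as reference while omitting the one it does.

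The size is modest. With categorical visits, the loss is one of alignment with the endpoint and of precision, about 5% to 9% on the Week 34 standard error, given 33 per arm and the assumed SD and correlation pattern. Material distortion of visit estimates requires two further conditions that the text leaves open: Week 26 kept as an outcome and time fitted as a straight line. It also requires an effect that does not grow linearly from Week 26.

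Severity is minor to moderate, because this is a secondary analysis outside the controlled testing sequence.

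**What to change.** In Protocol 10.5.7, or in the SAP that governs the core-phase analysis:

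- Make the pre-dose Week 26 score the reference for change and the baseline covariate. Use the 21-day window of SAP 2.1.1.2 as fallback, so that Week 24 serves only when Week 26 is missing.
- Limit the outcome visits to Weeks 28, 30, 32 and 34.
- Require a reference score and at least one score after Week 26 for entry.
- Fit visit as a categorical factor, with the treatment-by-visit interaction.
- Apply the same rules to the EQ-5D index, EQ-5D VAS and BDI-II.

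The cost is wording, plus refitting four models if the core-phase analysis used the Week 24 reference. No new data are needed. Because the core phase was unblinded on 10-May-2018 (SAP 1.2.3), any refit should be labelled as made after unblinding and shown beside the Week 24 version. If the core-phase SAP already adopted Week 26, a sentence recording the departure from Protocol 10.5.7 is enough.

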10.7 Interim analysis

The study has no planned interim analysis for efficacy.

10.8 Sample size calculation

Eligible patients will be stratified at randomization according to: LCI699 dose at Week 24 ($\leq 5\text{mg bid}$ vs. $> 5\text{mg bid}$); and history of pituitary irradiation (yes/no). It is estimated that 10 %, 40%, 10% and 40 % of randomized patients respectively will be in the 4 strata defined by two randomization stratification factors ($\leq 5\text{mg b.i.d}$ and Yes; $\leq 5\text{mg b.i.d}$ and No; $> 5\text{mg b.i.d.}$ and Yes; and $> 5\text{mg b.i.d.}$ and No) based on the following considerations:

1. LCI699 dose at week 24 ($\leq 5\text{mg b.i.d.}$ vs. $> 5\text{mg b.i.d.}$): Based on the data from the PoC study, 5mg b.i.d. is estimated to be the median LCI dose at week 24 for this phase 3 trial.
2. History of pituitary irradiation (Yes/No): Although supportive data is not available, it is assumed that approximately 20% of randomized patients will have a history of pituitary radiation.
3. In the absence of data to expect otherwise, it is assumed that these two stratification factors are independent of each other.

To detect a difference of 40% in complete response rate between 70% in LCI699 arm and 30% in placebo arm (equivalent odds ratio equals 5.444), a sample size of 33 patients per arm will be considered adequate based on a two-sided Cochran-Mantel-Haenszel (CMH) test at the 0.05 level with 87% power. Assuming that $\geq 50\%$ of enrolled patients will be eligible for randomization (mUFC \leq ULN at the end of the 24 week open-label LCI699 study period), 132 patients need to be enrolled into the study.

10.9 Power for analysis of key secondary variables

The analysis of the key secondary objective will be based on the 2-sided 95% confidence interval constructed using the Clopper-Pearson exact method. If the lower bound of this 95% confidence interval is $\geq 30\%$, the null hypothesis will be rejected and the complete response rate will be considered at least 30% after 24 weeks of treatment with LCI699.

The above testing on the key secondary objective will only be carried out if the null hypothesis for the primary objective is rejected. This sequential procedure will ensure preservation of the overall 2-sided type 1 error at 5%.

Assuming a 50% complete response rate (mUFC \leq ULN) at end of 24 weeks of LCI699 treatment, for 132 enrolled patients, there is 99.7% chance that the lower bound of 95% 2-sided C.I. of observed response rate (based on Clopper-Pearson Exact method) is larger than 30.0%.

11 Ethical considerations and administrative procedures

11.1 Regulatory and ethical compliance

This clinical study was designed, shall be implemented and reported in accordance with the ICH Harmonized Tripartite Guidelines for Good Clinical Practice, with applicable local regulations (including European Directive 2001/20/EC and US Code of Federal Regulations Title 21), and with the ethical principles laid down in the Declaration of Helsinki.

11.2 Responsibilities of the investigator and IRB/IEC/REB

The protocol and the proposed informed consent form must be reviewed and approved by a properly constituted Institutional Review Board/Independent Ethics Committee/Research Ethics Board (IRB/IEC/REB) before study start. Prior to study start, the investigator is required to sign a protocol signature page confirming his/her agreement to conduct the study in accordance with these documents and all of the instructions and procedures found in this protocol and to give access to all relevant data and records to Novartis monitors, auditors, Novartis Clinical Quality Assurance representatives, designated agents of Novartis, IRBs/IECs/REBs and regulatory authorities as required.

[figure not shown]
